10.1 Screening and Enrolment

Screening and Enrolment will be completed as detailed in Section 9, 9.4.

10.2 After Enrolment

Following patient enrolment, the following forms should be completed on the database using existing medical records/patient medical notes:

- i. Demographic Information
- ii. Clinico-pathological information
- iii. Prior Cancer Therapy

The diagnostic FFPE blocks available for the patient should be requested from pathology as soon as possible after the patient is enrolled. The sample information should be logged on the database and the sample sent to the GCP Laboratories using the sample kits provided.

10.3 First Lumbar Puncture / Ommaya Reservoir Aspiration Visit

The following procedures will occur at this visit:

- Blood sample collection (1 x 10ml EDTA blood tube and 1 x 10ml SERUM tube) this should be collected immediately before the CSF extraction procedure
- CSF extraction (1 x 10ml CSF tube and 1 x 3ml 5ml CSF tube) this should be carried
 out via Lumbar Puncture or Ommaya Reservoir aspiration as per standard procedure
 (atraumatic needles should be used unless discussed with PI & CI)
- Clinical complications questionnaire (completed by clinical staff via eCRF)

10.4 Follow-up - 28 days ± 7 days post-procedure (after CSF collection)

This visit can be carried out either at a routine visit or via phone call.

The following procedures will occur at this visit

Completion of the patient complications questionnaire.

The clinician should read the questions to the patient and record the patients answers either directly into the eCRF or onto the paper worksheet. If the answers are recorded on the paper worksheet, these should be transferred onto the database. The worksheet does not need to be sent to the LCTC but should be kept in the patient notes.

IRAS ID: 286155 Page **40** of **73**

The worksheet can be downloaded from the LCTC portal.

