3.1. Schematic the Study

Prior to enrolment

Patient Identification: Patients with CNS involvement secondary to breast cancer identified via breast and neuro-oncology/neuro-surgical departments, multi-disciplinary teams and clinics at involved UK centres.

- Obtain patient consent

Inclusion Criteria

- Informed Consent
- Male or female
- ≥16 years of age
- Any ER, PgR or HER2 status
- Newly diagnosed with BCBM*
- Progressive BCBM following either local or systemic treatment*
 - o or
- · Leptomeningeal disease

Exclusion Criteria

- Where the investigator considers it unsafe to undertake a lumbar puncture or perform an aspiration from the Ommaya reservoir
- Unable to comply with study procedures or give informed consent
- Where the investigator considers it not in the best interest of the patient to participate

At registration

- Patient enrolled on study

When scheduled

- Data collection and Routine/Diagnostic Tissue Collection

As soon as possible after procedure

 a) CSF extraction Procedure (along with blood sample collection pre-lumbar puncture/Ommaya Reservoir aspiration)

At routine visit or over the phone

- Post-procedure complications assessment for clinician (as soon as is feasible on a paper or eCRF)
- b) Post-procedure complications assessment **for patient** (28 days ± 7 days post-procedure at routine clinical visit or via phone

Paired Sample Collection (n = 20 if possible): Patients will be consented for a paired sample collection where they will be required to attend a second visit for lumbar puncture or Ommaya Reservoir CSF collection after 3 months of first CSF extraction or at disease progression (cranial or non-cranial). Follow procedures a), b) and c).

All samples sent to the GCP Lab for storage until sample collection end.

Samples sent to Cancer Research Lab in Leicester for analysis

Follow up end, Study Outcome Measures

IRAS ID: 286155 Page **15** of **73**

4. Roles and Responsibilities

Sponsor

The Sponsor is the University of Liverpool and is legally responsible for the study. They will formally delegate specific sponsoring roles to the Chief Investigator and Clinical Trials Centre.

Funders

North West Cancer Research is the lead funder for this study. It is funding the feasibility study the collection of 40 CSF samples of CSF, storage at GCP Laboratories and analysis at the University of Leicester.

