8.2 Secondary Outcomes

Objectives	Outcome Measure
The proportion of cases with an actionable mutation based on CSF cfDNA findings using the TARGET (Tumour Alterations Relevant for Genomics-Driven Therapy) database • The concordance between	These will be determined by identifying and quantifying (as a percentage or proportion) actionable mutations found in CSF cfDNA that match a specific gene database, namely TARGET (Tumour Alterations Relevant to Genomics Driven Therapy) gene database. This will be measured by quantifying the genomic
CSF cfDNA and brain metastases for detected mutations The concordance between plasma cfDNA and DNA from breast, extracranial and/or brain metastases for detected mutations (applicable for where brain metastasis has been resected) The concordance between plasma cfDNA and CSF cfDNA for detected mutations.	aberrations in both the CSF cfDNA and plasma cfDNA or tissue sample (primary, extracranial and/or CNS metastasis). The level of agreement will be measures as the number of aberrations observed in both samples as a proportion of all aberrations observed.
To determine the complications post lumbar puncture or aspiration of CSF from an Ommaya reservoir (This will not apply to patients undergoing a lumbar	1 x Patient questionnaire to record complications post- procedure.

IRAS ID: 286155 Page **30** of **73**

puncture at the time of a neurosurgical	Outcomes will be Percentage incidence, percentage
procedure).	severity experiences (i.e. headache, backache, pain
	down leg) and mean duration of experiences will be
	determined.
	1 x Clinician questionnaire to record complications
	post-procedure.
	eCRF will be used to record the date, the ease of the
	procedure complications and the need for intravenous
	fluid and/or analgesia
	Outcomes will be percentage / proportion of patients
	over total recruited patients.
	·

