9.5.1 Schedule of Study Procedures

	Screening & Registration (1st or 2nd visit)	First CSF Sample collection Visit*	2 nd CSF Sample Collection Visit*	Disease Progression OR Event driven Follow-up (e.g. Neurosurgery or relapse)**
Procedures				
Communication of study information & PIS	х			
Informed Consent	Х			
Check of Eligibility Criteria	х			
Confirmation of ER, PgR, HER2 status (primary breast cancer)***	х			
Data Collection				
Demographic Information	х			
Clinico-pathological information	х			
Prior Cancer Therapy (top line)	х			
Collection of data: At study entry and then subsequently when there is disease progression, treatment changes and	X			x

IRAS ID: 286155 Page **37** of **73**

death				
Diagnostic Biopsies				
Requesting and				
posting of FFPE				
Tissue:				
i) Collection of				
Primary Breast Biopsy				
and/or	X			v
ii) Collection of non-	*			X
CNS				
recurrent/metastatic				
tissue and/or				
ii) Collection of CNS				
Biopsy				
Blood and CSF				
Collection of blood				
samples:				
1 x 10ml EDTA blood				
tube		X	X	
1 x 10ml SERUM tube		^	^	
(prior to lumbar				
puncture with				
atraumatic needle)				
Lumbar Puncture				
Collection of:				
1 x 10ml CSF tube		X	x	
1 x 3ml - 5ml CSF			Α	
tube				
Questionnaire				
(Completed on				
patient's discharge)				

IRAS ID: 286155 Page **38** of **73**

Clinical complications			
questionnaire (clinical			
staff to complete on	Х	X	
eCRF)			
Questionnaire (28			
days ± 7 days post-			
lumbar puncture)			
Patient complications			
questionnaire (patient	Х	x	
to complete via phone	^	^	
or at routine visit)			

^{*}For initial and sequential CSF sample (at disease progression or if patient is well 3 months after first CSF extraction). This will be mentioned on the Patient Information Sheet and Consent Form.

IRAS ID: 286155 Page **39** of **73**

^{**}Data will be collected for all patients if there are changes in their progression, treatment or in the event of death up until study closure or patient withdrawal.

^{***}ER, PgR and HER2 status of all CNS and non-CNS metastatic (where available) collected will documented.

10. Procedures for all patients

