12.5.1 Reference Safety Information used to Assess Expectedness

This study involves collecting CSF via lumbar puncture (with atraumatic needles) or from aspiration of CSF from in situ Ommaya reservoirs form patients with CNS involvement secondary to breast cancer. For the majority of patients this will be an extra procedure, although in a small number of cases it will be performed at disease progression or following continued patient response (i.e. if disease is not progressing). Potential risks and side effects of the procedure include infection (rare), nerve root irritation (in a minority of patients), headaches, nausea/vomiting and back pain.

IRAS ID: 286155 Page **50** of **73**

To minimise risk lumbar punctures will be performed using appropriate local anaesthesia by clinicians experienced in the procedure. Furthermore, atraumatic needles will be used which are associated with significantly less side effects than conventional needles for lumbar punctures. Where patients are undergoing a neurosurgical procedure, the lumbar puncture will be carried out once patient has been anaesthetised so reducing any side effects. Patients will be followed up to understand the side effects if any that occur post procedure²².

The information to be used for expectedness assessment for PRIMROSE CSF Study is below:

Event	Lumbar Puncture or	<pre><incidence frequency="" of<="" pre="" prevalence=""></incidence></pre>
	Ommaya Reservoir	event>*
	aspiration	
Back Pain at the time of	Lumbar Puncture	Common
injection (Bleeding, swelling		
and bruising may occur)		
Post-procedure headache	Lumbar Puncture	Common, possibly begins immediately or a
(can be associated with		few days after procedure and usually lasts
nausea and vomiting)		less than 1 week
Persisting back pain	Lumbar Puncture	Very rare
Nerve root irritation (tingling	Lumbar Puncture	Rare
or pain down the back of		
your legs)		
Brainstem herniation	Lumbar Puncture	Very very rare
Post-procedure infections ^a	Ommaya Reservoir	Very very rare
	aspiration	

^{*}These side-effects are listed on the following sites:

https://www.mayoclinic.org/tests-procedures/lumbar-puncture/about/pac-20394631

https://www.nhs.uk/conditions/lumbar-puncture/

^aPlease see section 7; 7.2 Exclusion Criteria. Where the investigator deems it unsafe to perform CSF extraction due to high risk of infection, the procedure will not be conducted.

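### Patient-reported complications rest on one interview at day 21 to 35, with no scheduled collection between discharge and then, and no pre-procedure symptom item specified in the protocol

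*Protocol*

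**What the plan says.** All references are to the Protocol.

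- **Outcome.** Complications after lumbar puncture or Ommaya aspiration are a secondary objective (Section 5.4.2). Section 8.2 takes incidence, severity and mean duration from a single patient questionnaire, and names the symptoms: "severity experiences (i.e. headache, backache, pain" down the leg. A clinician questionnaire records the ease of the procedure, complications, and need for intravenous fluid or analgesia. Patients punctured during neurosurgery are outside this outcome.
- **Patient questionnaire.** Section 10.4 sets the contact at 28 ± 7 days, says "This visit can be carried out either at a routine visit or via phone call", and lists one task: "Completion of the patient complications questionnaire".
- **Clinician questionnaire.** The schedule in Section 9.5.1 has it completed on the "patient's discharge". The schematic in Section 3.1 is looser: "as soon as is feasible on a paper or eCRF".
- **Expected course.** The table in Section 12.5.1 rates post-procedure headache as common. It may begin at once or a "few days after procedure and usually lasts" less than one week. The other event rated common is back pain at the time of injection.
- **Before the procedure.** The enrolment forms cover demographics, clinico-pathological information and prior therapy (Section 10.2). The collection visits list bloods, CSF and the clinician form (Sections 10.3 and 10.6). None of these, nor the schedule, names a symptom item.
- **Adverse events.** All are reportable from the puncture to the follow-up contact (Section 12.6). They are graded (12.3), assessed for causality (12.4), entered on a form whether or not serious (12.8.1) and sent within seven days of the site becoming aware (12.11).

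**The concern.** The outcome and the schedule do not fit each other. Incidence, severity and duration of an event that usually lasts days are asked about once, weeks later. The only earlier study form is completed at or near discharge, before a delayed headache would have started.

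The second difficulty is the missing starting point. Eligible patients have newly diagnosed or progressive brain metastases or leptomeningeal disease (Section 7.1), and a second collection may be triggered by disease progression (Section 10.6). Headache and back pain before the needle goes in are plausible in such patients. If they are asked at day 28 about headache since the procedure, the protocol specifies nothing against which to judge whether it was new.

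At stake is the credibility of the complication rate. For most patients the procedure is additional to care (Section 5.3.1) with no direct benefit expected (5.3.2), and the study is meant to inform later ones. An analysis plan written later cannot recover a symptom status that was never collected.

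**Working it through.** **1. The plan's own figures.** The interview window is 28 − 7 = day 21 to 28 + 7 = day 35. The only precision figure is the 6% standard error for 70 patients in Section 13.2: √(0.5 × 0.5 / 70) = 0.0598, which reproduces.

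**2. Where a delayed headache falls.** Assumptions: a few days means onset on day 2 to 5, and duration is 1 to 7 days (the table says usually under a week).

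- End day = onset + duration: from 2 + 1 = day 3 to 5 + 7 = day 12.
- From end of headache to interview: from 21 − 12 = 9 days to 35 − 3 = 32 days.
- From onset to interview: from 21 − 5 = 16 days to 35 − 2 = 33 days.

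**3. What is in place at each point.**

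| Time | Scheduled study collection | What it can catch |
|---|---|---|
| Before the procedure | Bloods; no symptom item named | – |
| Discharge | Clinician questionnaire | Back pain at injection; immediate headache |
| Discharge to day 21 | None; adverse event forms if the site learns of an event | Events reported by the patient or found in notes |
| Day 21–35 | Patient questionnaire | Recalled symptoms |

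**4. Illustration of size.** None of these inputs is in the documents. Let *p* be the true rate of new headache, *s* the share recalled, and *b* the share of the remaining patients who report a pre-existing headache as a complication. Then

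reported rate = *p·s* + (1 − *p·s*)·*b*.

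With *s* from 0.7 to 1 and *b* from 0 to 0.2:

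| True *p* | Lowest (*s* = 0.7, *b* = 0) | Highest (*s* = 1, *b* = 0.2) | Error, percentage points |
|---|---|---|---|
| 10% | 0.10 × 0.7 = 7% | 0.10 + 0.90 × 0.2 = 28% | −3 to +18 |
| 20% | 0.20 × 0.7 = 14% | 0.20 + 0.80 × 0.2 = 36% | −6 to +16 |
| 30% | 0.30 × 0.7 = 21% | 0.30 + 0.70 × 0.2 = 44% | −9 to +14 |

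The two errors oppose each other and can nearly cancel. With *p* = 0.3, *s* = 0.7 and *b* = 0.1 the reported rate is 0.21 + 0.79 × 0.1 = 28.9%, an error of −1.1 points.

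**5. What a baseline item would do.** It aims at *b* = 0. For *p* = 20% the range then narrows from 14–36% to 14–20%, leaving recall loss only.

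**The case against.** The strongest answer is Section 12. A reader might infer that nothing structured is recorded between discharge and day 21. That is wrong: every adverse event in exactly this window belongs on a form, with severity grade, causality and standard terms. Two limits remain. Section 12.8 relies on events coming to staff attention through visits, notes or the participant, and no study contact is scheduled before day 21. And Section 8.2 does not name the adverse event forms as a source for this outcome.

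A reader might also infer that no pre-procedure symptoms are recorded at all. The clinico-pathological form and both questionnaires are not shown, and the questionnaire could ask about new or worsened symptoms. The text supports only that the protocol specifies no such item.

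Nor does it follow that attribution is impossible, because the causality scale in Section 12.4 asks the investigator to weigh the patient's clinical condition. That helps the adverse event data. It does not help the patient-reported rate, and the judgement itself would be better with a recorded baseline.

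Three further points stand. The discharge form can catch immediate headache and back pain at injection, so not all complication data are late recall. Patients who die or deteriorate before day 28 may give no questionnaire but are not lost to safety data, since deaths and serious events are notified within 24 hours (12.10, 12.11). And a downward bias in severity or duration, though tempting to assert, is not shown: recall loss lowers incidence, but its effect on the other two is uncertain.

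**Conclusion.** The concern holds in a limited form. The patient-reported incidence, severity and duration depend on one recalled interview at day 21 to 35. No scheduled or active collection covers the period in which a delayed headache would usually occur, and no pre-procedure symptom item is specified.

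The documents do not allow the net direction or the size of the error to be stated. The illustration shows only that, under moderate assumptions, it can reach or exceed the 6-point standard error the plan treats as adequate. Unlike that standard error, it does not shrink with more patients.

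This is a minor point. It affects one descriptive secondary outcome in a single-arm study without hypothesis tests. It does not touch the recruitment-based feasibility criterion or the cfDNA objectives, nor patients whose puncture is done at neurosurgery. It is worth acting on because the remedy is cheap and works only if in place before the procedure.

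**What to change.** 1. In Sections 9.5.1, 10.3 and 10.6, add one CRF line, completed at the blood draw just before each CSF collection, recording presence and severity of headache, back pain and leg pain.
2. In Section 8.2, define incidence as symptoms that are new or worse than on that line.
3. In Section 8.2, name the adverse event forms as a second source, using onset and resolution dates alongside the day-28 questionnaire for incidence and duration. Check that the ordinary adverse event form holds both dates: Section 12.8.1 lists date of onset only for the serious event form.

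The cost is one extra CRF item per collection visit and the matching protocol and eCRF revision. No visit or call is added.

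Optional: a symptom card given at discharge and read back at the existing day-28 contact would also address recall. It adds patient burden and staff handling, and as a new patient-facing document would probably need ethics approval, so the point does not depend on it.

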10.5 Disease Progression / Event driven Follow-up

If there are no changes in patient's condition, disease or treatment then there is no requirement to provide follow-up data.

In the event of patient disease progression, treatment changes or in the event of death, the following forms should be completed on the database using existing medical records/patient medical notes:

- i. Disease progression
- ii. Treatment changes
- iii. Death data (cause and date)

In the event of new tissue samples being collected either at the point of neurosurgery or when there is a change in patient's condition, disease or treatment, the FFPE blocks available for the patient should be requested from pathology. The sample information should be logged on the database and the sample(s) sent to the GCP Laboratories using the sample kits provided.

10.6 Second Lumbar Puncture / Ommaya Reservoir Aspiration Visit

Where a patient is undergoing a second CSF collection, this should be carried out either at disease progression or if the patient remains well – after 3 months of the first CSF extraction.

The following procedures should occur at this visit:

- Blood sample collection (1 x 10ml EDTA blood tube and 1 x 10ml SERUM tube) this should be collected immediately before the CSF extraction procedure
- CSF extraction (1 x 10ml CSF tube and 1 x 3ml 5ml CSF tube) this should be carried
 out via Lumbar Puncture or Ommaya Reservoir aspiration as per standard procedure
 (atraumatic needles should be used unless discussed with PI & CI)
- Clinical complications questionnaire (completed by clinical staff via eCRF)

Following this visit, the Follow-up visit should take place as per Section 10.4

IRAS ID: 286155 Page **41** of **73**

10.7 Participant Discontinuation/Withdrawal

In consenting to the trial, participants agree to all trial activities including sample collection and data collection. Every effort should be made to facilitate the completion of these for every recruited participant. If it is not possible to complete these activities (or it is deemed inappropriate) the reasons why should be documented.

Patients may be withdrawn from the study for any of the following reasons:

- Patient (or their designated legal representative, where applicable) withdraws consent.
- Where the investigator deems it not in the patient's best interest to continue on the study
- Death
- Any change in the patient's condition which results in contraindication to collection procedures or causes the patient to fall under the exclusion criteria

Data to be collected at the time of discontinuation includes the date of discontinuation and reason for discontinuation.

If a patient wishes to withdraw, the value of existing samples should be explained, and permission sought to continue retaining and using these samples. Generally, samples will be retained unless it is specifically requested for them not to be. Upon withdrawal, the LCTC and TMG should be informed in writing immediately (ideally via E-mail) and no further samples or data should be collected.

Permission will be sought to use all samples collected thus far in the case of withdrawal. However, patients have the right to request that any samples which have not yet already been used in research to be disposed of. If a patient explicitly states that this is their wish, then the LCTC should be informed immediately in writing and the samples will be destroyed.

In some cases, it will be impossible to destroy the samples without affecting other samples as they will have been irreversibly linked to others (such as in cases of tissue microarrays being produced or plasma samples being pooled). In these cases, the sample itself will not be destroyed; however, information linking the sample to any patient identifiers will be destroyed, deleted or censored as appropriate to eliminate the link and make the sample unidentifiable.

IRAS ID: 286155 Page **42** of **73**

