	Leptomeningeal disease	
	5. Informed Consent	
Exclusion Criteria:	Where the investigator considers it unsafe to undertake a lumbar	
	puncture or perform an aspiration from the Ommaya reservoir	
	Unable to comply with study procedures or give informed consent	
	3. Where the investigator considers it not in the best interest of the	
	patient to participate	
Study Centres and	Open to all UK NHS centres involved in the medical or surgical care of	
Distribution:	patients with breast cancer	
Patient Study	The patients will be followed up until death, withdrawal of consent or study	
Duration:	closure, whichever is sooner.	
Study Duration	2 years	

IRAS ID: 286155 Page **13** of **73**

Primary objectives

- To determine the feasibility of recruiting patients to undergo lumbar puncture or aspiration of Ommaya Reservoir to enable the collection of cerebrospinal fluid.
- To determine the molecular aberrations, present within CSF cell-free DNA (cfDNA).

Secondary objectives

To determine

- The proportion of cases with an actionable mutation based on CSF cfDNA findings using the TARGET (Tumour Alterations Relevant for Genomics-Driven Therapy) database.
- The concordance between CSF cfDNA and brain metastases for detected mutations (applicable where brain metastasis has been resected).
- The concordance between plasma cfDNA and brain metastases for detected mutations (applicable where brain metastasis has been resected).
- The concordance between plasma cfDNA and CSF cfDNA for detected mutations.
- The complications post-lumbar puncture or aspiration of CSF from an Ommaya reservoir (This will not apply to patients undergoing lumbar puncture at the time of neurosurgical procedure).

Exploratory objectives

 To compare the genomic landscape between paired CSF paired samples (i.e. where collected at different time points)

IRAS ID: 286155 Page **14** of **73**

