10.9 Loss to Follow-up

A participant will be considered lost to follow up if they fail to return for scheduled visits and cannot be contacted by the site research team.

If a participant fails to attend/facilitate a required study visit the following actions must be taken:

- Site will attempt to contact the participant and reschedule the missed visit and advise the
 participant on the importance of maintaining the assigned visit schedule.
- Before a participant is deemed to be lost to follow up, site research staff will make every effort to regain contact with the participant (i.e. 3 telephone calls and, if necessary, a headed letter to last known address). These efforts should be recorded in the patient medical notes.
- If the participant continues to be unreachable, they should be considered withdrawn from the study with a primary reason of lost to follow up and this should be recorded on the appropriate CRF.

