12.6 Time Period for Recording Adverse Events

All adverse Events (AEs) should be reported from the time of first lumbar puncture until the follow up visit (28 days +/- 7 days post-procedure). For patients undergoing a second lumbar puncture, AEs should also be reported from the time of the second lumbar puncture until the follow-up visit (28 days +/- 7 days post-procedure). Depending on the nature of the event the reporting procedures

IRAS ID: 286155 Page **51** of **73**

below should be followed. Any questions concerning AE reporting should be directed to the LCTC in the first instance.

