12.8.2 Follow-up After Adverse Events

All reportable adverse events should be followed until satisfactory resolution or until the investigator responsible for the care of the participant deems the event to be chronic or the patient to be stable.

When reporting "serious" safety events the investigator responsible for the care of the participant should apply the following criteria to provide information relating to event outcomes:

- resolved
- resolved with sequelae (specifying with additional narrative)
- not resolved/ongoing
- ongoing at final follow-up
- fatal or unknown.

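### Section 10.7 does not say that its stop on data applies only to withdrawal of consent, so a site could stop follow-up in patients discontinued for other reasons

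*Protocol*

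**What the plan says.** Section 10.7 lists four reasons for which a patient may be withdrawn: withdrawal of consent, the investigator's view of the patient's best interest, death, and a change in condition that "results in contraindication to collection procedures or causes the patient to fall under the exclusion criteria". Only the first is withdrawal of consent. Two paragraphs later, in text that begins with a patient who wishes to leave, it says that upon withdrawal the trials centre and management group are to be told and "no further samples or data should be collected".

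Four other places bear on how long data are collected:

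- Section 3, Overview (patient study duration): "The patients will be followed up until death, withdrawal of consent or study" closure, whichever comes first.
- Section 9.5.1, footnote on event-driven data: collected on changes in progression or treatment "or in the event of death up until study closure or patient withdrawal".
- Section 10.9: after failed attempts at contact, "they should be considered withdrawn from the study with a primary reason of lost to follow up".
- Section 10.5: on progression, treatment change or death, "the following forms should be completed on the database using existing medical records/patient medical notes".

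The safety section has its own time limits. Under 12.6, adverse events "should be reported from the time of first lumbar puncture until the follow up visit" at 28 ± 7 days. Under 12.8.2, "All reportable adverse events should be followed until satisfactory resolution" or until judged chronic or stable. Neither mentions withdrawal.

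**The concern.** The protocol uses one word for two situations. In one, a patient takes back permission, and data collection has to stop. In the other, a patient can no longer safely have a lumbar puncture, or the investigator thinks further procedures unwise, but consent stands. In the second case there is no reason to stop the questionnaire after a procedure already done, or to stop reading the medical record.

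Section 10.7 has no separate category for stopping procedures while keeping follow-up. The only data it names at discontinuation are the date and the reason. Site staff could therefore take the stop to cover every reason on the list.

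The exposed outcome is the patient-reported part of the complications objective in 8.2 (incidence, severity, duration). The patients concerned may not be typical. The exclusion criteria in 7.2 include an unsafe puncture, inability to comply and the patient's best interest, and a patient who does badly after a study puncture could meet any of them. A complication could then lead to the withdrawal that ends its own follow-up. A questionnaire that was never given cannot be recovered at analysis.

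**Working it through.** No figure in the protocol settles this point, so the check is mainly a comparison of texts.

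**1. Which reasons does the stop cover?**

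| Reason | Overview: follow-up ends? | 9.5.1 footnote: data end? | 10.7 stop, read broadly | 10.7 stop, read narrowly |
|---|---|---|---|---|
| Consent withdrawn | Yes | Yes | Yes | Yes |
| Investigator decision | No | Yes, if withdrawal has its 10.7 meaning | Yes | No |
| Contraindication or exclusion criterion | No | Yes, if withdrawal has its 10.7 meaning | Yes | No |
| Lost to follow-up (10.9) | No | Yes, if withdrawal has its 10.9 meaning | Yes | No |
| Death | Yes | Death data requested | Yes, against 10.5 | No |

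The death row shows that the broad reading cannot be meant for every listed reason, because 10.5 asks for date and cause of death. The text does not say where the rule stops. The narrow reading agrees with the Overview throughout. The broad reading conflicts with the Overview on three rows and, once a procedure has been done, with 12.6 and 12.8.2.

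**2. When is the questionnaire at risk?** The window is 28 ± 7 days after the procedure (10.4), so it closes at day 28 + 7 = 35. Only a discontinuation after a procedure and before the form is completed, at the latest day 35, can cost that form. If 3 months is taken as 91 days (an assumption), a contraindication found at a 3-month second collection comes 91 − 35 = 56 days, or 8 weeks, after the first form's window has closed. It would cost only records-based data. A contraindication found at early progression could cost the form as well.

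**3. What stays protected?** The clinician complications form is completed at the procedure visit (10.3). Adverse event reporting (12.6), follow-up to resolution (12.8.2), serious event follow-up (12.11.1) and death notification (12.10) carry no exception for withdrawn patients. The verdict in 13.4 counts recruited patients. The exposed items are therefore the 28-day patient form and the progression and treatment data under 10.5.

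**4. What would a loss do?** The protocol gives no rate of discontinuation for reasons other than consent, so the figures below are illustrations on assumed rates.

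- Precision. Section 13.2 states a conservative standard error of 6% with 70 patients: √(0.5 × 0.5 / 70) = 0.0598, which reproduces it. If 10% of forms were lost, n = 63 and √(0.25 / 63) = 0.0630. If 20% were lost, n = 56 and √(0.25 / 56) = 0.0668. The loss is modest.
- Bias. Suppose 20% of patients who stay have a complication. If 10% are discontinued and half of those have one, the true rate is 0.9 × 0.20 + 0.1 × 0.50 = 0.23, against 0.20 observed. If the discontinued have a 30% rate, the true rate is 0.9 × 0.20 + 0.1 × 0.30 = 0.21. If both groups have the same rate, there is no bias.

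The direction is plausible. The size is not known.

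**The case against.** The strongest reply is that 10.7, read in context, already means what it should. The stop sits in a paragraph that opens with a patient who wishes to leave and asks permission to keep samples. The next paragraph concerns the patient's right to have samples destroyed. Neither fits an investigator's decision. The opening of 10.7 also asks for every effort to complete study activities and for reasons to be documented where one cannot be done, so a patient unfit for a second puncture can be recorded as such and stay in the study. The list is permissive: patients may be withdrawn, not must be. Under 10.9, a patient who cannot be reached cannot answer a questionnaire whatever 10.7 says. Progression and treatment data are not outcomes in section 8.

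Most of this stands. The narrow reading is the more natural one, and it limits how often the problem would arise. What remains is that the narrow reading is never stated, that the 9.5.1 footnote and 10.9 use the term more widely, and that the Overview says something different from the footnote for patients whose consent still stands.

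Two stronger inferences should be resisted. A reader might infer that 10.7 orders all data to stop for every withdrawn patient; its context and 10.5 speak against that. A reader might also take the 20 planned paired collections as the number at risk. That is a target for second samples, to be met if possible, and does not count discontinued patients.

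**Conclusion.** The concern holds as a gap in wording with a small consequence. The term is used inconsistently, and a site that applies the stop to discontinuations not based on consent could lose the 28-day patient questionnaire when discontinuation falls between a procedure and about day 35, and records-based progression and treatment data after that.

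Two assumptions carry the conclusion: that some sites would read the rule broadly, and that some patients are discontinued for other reasons in that window. The protocol gives no rate for either. The number of patients is likely small and cannot be quantified. Bias in the complications estimate is possible if complications cause discontinuation, but the documents do not show that it will occur. A reader might infer that safety reporting or the feasibility result is compromised; the separate rules in section 12 and the recruitment-based criterion in 13.4 leave both largely untouched. Severity is low.

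**What to change.** - **10.7:** limit the stop on samples and data to withdrawal of consent. Add that patients discontinued for any other reason stop CSF procedures only, and keep the 28-day questionnaire after any procedure done, adverse event follow-up under 12.6 and 12.8.2, and event-driven data under 10.5.
- **9.5.1 footnote:** replace *patient withdrawal* with *withdrawal of consent*, to match the Overview.
- **10.9 (optional):** add that loss of contact ends visits and questionnaires, while records-based data under 10.5 continue.

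The cost is a sentence or two in 10.7, a short change to the footnote and, if wanted, one sentence in 10.9. No visit, test or patient is added.
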